12.5 Total volume of blood removed

The total volume of blood taken from each volunteer in the trial will be about 184.5 mL (Table 7; PBMC-only subjects) or 537 mL (Table 8; PET subjects). Additional blood samples for assay of ASN51, PBMCs, or for laboratory safety tests may be taken as described in section 12.2. No more than an extra 80 mL of blood will be taken from any PBMC-only subject, and no more than an extra 30 mL of blood from any PET subject, unless medically indicated for safety reasons.

Table 7: Planned blood volume (PBMC-only subjects)

Test	Planned number of tests	Volume (mL)	Total planned blood volume (mL)
Haematology	6	2	12
Clinical chemistry	6	3.5	21
Coagulation	6	3	18
Serology (and FSH)	1	3.5	3.5
Pharmacokinetics	30	2	60
PBMC sampling	14	5	70
		Total	184.5 mL

Table 8: Planned blood volume (PET subjects)

Test	Planned number of tests	Volume (mL)	Total planned blood volume (mL)
Haematology	6	2	12
Clinical chemistry	7	3.5	24.5
Coagulation	6	3	18
Serology	1	3.5	3.5
Arterial	3	120	360
Pharmacokinetics	32	2	64
PBMC sampling	11	5	55
		Total	537 mL

13 Trial materials

13.1 Identity of test product(s)

Immediate-release [REDACTED] containing [REDACTED] ASN51 will be provided to the HMR pharmacy by Asceneuron S.A, and will be packed and dispatched in containers.

Full details of ASN51 are included in the IB¹ and IMPD²⁷.

The sponsor will provide to HMR a certificate of analysis, and a Certificate of GMP Compliance for the test product for HMR's Qualified Person to release batches of IMP.

13.2 Packaging and labelling

The trial medication will be packaged and labelled by the HMR Pharmacy, in accordance with The Rules Governing Medicinal Products in the European Union, Volume 4: Good Manufacturing Practice (GMP), and with HMR's Manufacturing Authorisation for IMPs (MIA(IMP)). The IMP labels will include all the information required by Annex 13 to GMP¹³.

13.3 Storage and accountability of IMP

The IMP will be stored and accounted for according to GMP and HMR SOPs.

At the end of the trial, all unused IMP supplies will be returned to the sponsor or destroyed in accordance with the sponsor's instructions.

13.4 Non-investigational medicinal product

The radioligand [¹⁸F]-IMA601 (non-IMP) will be prepared by Invicro.

Product name: [¹⁸F]-IMA601 (also known as [¹⁸F]OGA1)

Dosage form: sterile solution for injection

Effective dose: maximum 2.33 mSv for each PET scan (including components from both the PET [2.05 mSv] and CT scans [0.28 mSv])

Specific activity: will not exceed 100 MBq for each PET scan

Route of administration: IV bolus

Manufacturer/source of procurement: Invicro*

* cGMP grade precursor will be procured from an external commercial source

Full details are included in the [¹⁸F]-IMA601 non-IMPD²⁸.

13.5 Other trial supplies

Supplies of containers to be used to package IMP (eg bottles, vials, syringes), components to be used in the assembly of a dose (eg labels), and excipients to be used in the preparation of the IMP (eg sterile saline solution) will be placed in quarantine on receipt by HMR, pending assessment and release by Pharmacy Quality Control.

14 Adverse events

14.1 Definitions of adverse events

Adverse event (AE)

Any untoward medical occurrence in a patient or clinical trial subject administered a medicinal product and which does not necessarily have a causal relationship with that treatment.

Adverse drug reaction (AR)

All untoward and unintended responses to an IMP related to any dose administered. Note that, according to the ICH Guideline for Good Clinical Practice (ICH GCP), the phrase 'response to an IMP' means that a causal relationship between the medicinal product and an AE is at least a reasonable possibility, ie a relationship cannot be ruled out.

Unexpected AR

An AR, the nature or severity of which is not consistent with the applicable product information (eg IB for an unauthorised investigational product, or summary of product characteristics for an authorised product).

Serious adverse event (SAE) or serious adverse drug reaction (SAR)

An AE or AR that:

- is fatal;
- is life-threatening;
- requires or prolongs inpatient treatment;
- results in persistent or significant disability or incapacity; or
- is a congenital anomaly or birth defect.

Note that:

- the term 'life-threatening' in the definition of 'serious' refers to an event or reaction in which the patient was at risk of death at the time of the event; it does not refer to an event or reaction which hypothetically might have caused death had it been more severe; and
- in accordance with the ICH Guideline on Clinical Safety Data Management: Definitions and Standards of Expedited Reporting, events or reactions that are not immediately life-threatening or may not result in death or hospitalisation, but might jeopardise the subject or require intervention to prevent one of the other outcomes listed above, should usually be considered serious.

Significant AE or AR

Any SAE or SAR, or an AE or AR which is not serious but is otherwise significant. The following should normally be considered significant:

- a marked haematological or other laboratory abnormality;
- an AE or AR that leads to an intervention, including withdrawal of drug treatment, dose reduction or significant additional concomitant therapy; or
- any AE or AR that the investigator considers to be significant.

14.2 Procedures for recording adverse events

Subjects will be carefully monitored for AEs. The investigator or delegate will question the subjects about AEs using a non-leading question, such as 'How are you feeling?'. The investigator will also record AEs reported spontaneously by the subjects. Clinically significant changes in the findings of physical examination, and clinically significant abnormalities in the results of objective tests (eg laboratory variables, x-ray, ECG) may also be recorded as AEs. The investigator will use the following criteria when deciding whether to report an abnormal result as an AE.

1. The test result is associated with accompanying symptoms.
2. Results of additional diagnostic tests cause concern or necessitate medical intervention.
3. As a consequence of the test result, the dose administered to the subject is changed, the subject is withdrawn, or the subject is given concomitant treatment.
4. The investigator considers the result to constitute an AE.

If any of the above criteria are met, the investigator will report the result as an AE.

A record will be kept in the source documents of all AEs as reported, whether believed to be related or unrelated to the treatment. The record will include the following.

- **Clinical symptoms:** a simple, brief description.
- **Date and time of onset and end:** of clinical symptoms.
- **Frequency:** constant or intermittent.
- **Severity.** The following categories will be used:

Mild: the AE does not interfere with the volunteer's daily routine, and does not require intervention; it causes slight discomfort.

Moderate: the AE interferes with some aspects of the volunteer's routine, or requires intervention, but is not damaging to health; it causes moderate discomfort.

Severe: the AE results in alteration, discomfort or disability which is clearly damaging to health.

- **Relationship to treatment:** The assessment of relationship of AEs to the administration of IMP is a clinical decision based on all available information at

the time of the completion of the case report form. The following categories will be used.

Unrelated

- The AE is clearly not related to the study drug/procedure, beyond a reasonable doubt.

Unlikely related

- The AE is doubtfully related to the study drug/procedure.

Possibly related

- The AE may be related to the study drug/procedure.

Probably related

- The AE is likely related to the study drug/procedure.

Definitely related

- The AE is clearly related to the study drug/procedure.

For the purposes of reporting to regulatory agencies, AEs deemed ‘definitely related’, ‘probably related’ or ‘possibly related’ will be considered related to study treatment; and those deemed ‘unrelated’ or ‘unlikely related’ are considered unrelated to study treatment.

AEs listed as related are considered to have a suspected ‘reasonable causal relationship’ to the study drug/intervention (ICH E2A). The expression ‘reasonable causal relationship’ is meant to convey in general that there are facts (evidence) or arguments to suggest a causal relationship.

- **Action taken:** none, drug treatment, subject withdrawn, other (specified).
- **Outcome:** recovered/resolved, recovering/resolving, not recovered/not resolved, or unknown.

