A total exposure of 6.99 mSv falls into category IIb (upper limit 10 mSv) of the guidance published by the International Committee for Radiation Protection (ICRP). There is no dose limit for research purposes in the UK. However, as in many member states in the EU, the UK follows the ICRP 62 guidance that provides a guideline of 10 mSv (or less) per study where research subjects are not expected to benefit personally¹².

Magnetic resonance imaging (MRI) to delineate brain anatomy will be done in this study to aid PET image analysis. There are no known risks to subjects associated with MRI scanning, provided that they have no contraindications to MRI as listed in the exclusion criteria (section 9.3, exclusion criterion 36). Potential risks associated with metallic implants will be mitigated by administration of a questionnaire and careful screening.

Risk associated with arterial cannulation (PET subjects only)

Before the PET-CT scan, subjects will have a cannula inserted into the radial artery by qualified staff using aseptic technique under local anaesthesia. That insertion may be uncomfortable, cause minor local bleeding and bruising, and can rarely lead to complications (eg, a blood clot could form around the cannula). Most people have no after-effects of cannulation. However, very occasionally, it may cause a small scar. Very rarely, more serious complications can occur, although these usually occur when the radial artery is cannulated in sick people for therapeutic purposes, rather than in healthy subjects for research purposes.

Assessment of the patency of collateral arterial circulation will be assessed at screening and at each imaging session using Allen's test, to minimise the risk of complications.

Use of healthy young male volunteers (PET subjects only)

Despite the potential risk of testicular toxicity, radiation exposure, and repeated arterial blood sampling described above, healthy young volunteers are the most suitable population for the present study, because they:

- have no confounding pathology (eg vascular disease), or concomitant medicine use (eg aspirin), that would contraindicate arterial cannulation, and are better able to tolerate the procedure.
- are better suited to tolerate repeated blood draws for PK and PBMC analyses (to a maximum total of 537 mL; see section 12.5).
- are better able to tolerate repeated PET scans.

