8.4 Stopping criteria

8.4.1 *Trial stopping criteria*

The trial will be stopped if either of the following occurs:

- 1 or more SAEs considered to be at least possibly related to study treatment; or
- 2 or more severe or clinically significant AEs considered to be at least possibly related to study treatment at any dose level.

If, after an internal safety review, it is appropriate to restart the trial, a substantial amendment will be submitted to the MHRA and research ethics committee (REC). The trial will not restart until the amendment has been approved by the MHRA and REC.

8.5 Criteria for proceeding to Group 2

8.5.1 *Review of data by the Safety Review Group*

Before proceeding to Group 2, the SRG will review the safety, tolerability and PK data from Group 1. The SRG will include (as a minimum) the principal investigator (or medically qualified delegate) and the sponsor's medically qualified representatives (Primary Medical Officer and the Head of Translational Medicine [or delegate]). Each dose decision will be made and documented in line with HMR SOPs. All data used to support dose selection will be quality checked.

The SRG will review safety, tolerability, and PK data up to 6 days after the final dose (Day 20) from all subjects dosed in Group 1. In the event of a subject withdrawal prior to Day 20, all available safety, tolerability, and PK data from that subject will be included in the SRG review. The review will include (as a minimum) data from at least 4 evaluable subjects. An evaluable subject is one who completes dosing and has undergone procedures until 6 days after final dosing (Day 20), and had no major protocol deviations.

The data reviewed will include, as a minimum:

- AEs and SAEs, including description, frequency, intensity, onset, duration, and relationship to treatment
- vital signs

- 12-lead safety ECG
- laboratory safety tests
- PK parameters

Group 2 will proceed only if the following are true.

- The safety and tolerability of [REDACTED] ASN51 QD are deemed acceptable
- In any individual subject, C_{max} and AUC_{24} after [REDACTED] ASN51 QD are predicted not to exceed the following limits, which are based on the NOAEL in 4-week toxicology in dogs (as detailed in sections 6.2.1).

C_{max} : 3,000 ng/mL	AUC_{24} : 25,000 ng·h/mL
-------------------------	-----------------------------

The trial will be stopped if any of the criteria in section 8.4.1 are met.

9 Trial population

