## **19 ATTACHMENTS**

### **19.1 Table of contents for data display specifications**

For overall page layout refer to Appendix C: Sample page .

The numbering in the tables below will take precedence over the numbering in the shells.

The following tables and figures will be produced (templates provided in Sections 19.2.1 and 19.2.2):

Table	Description	Population	Source Listing	Template (Shells below)
10.1	Summary of subject disposition	Safety	16.2.1.2 16.2.1.3 16.2.3.1	T_SD1
14.1	DEMOGRAPHIC DATA			
14.1	Summary of demographic characteristics	Safety	16.2.4.1	T_DM1
14.2	PHARMACOKINETIC AND PHARMACODYNAMIC DATA			
14.2.1.1	Summary of ASN51 plasma pharmacokinetic concentration-time data [units]	PK analysis	16.2.6.1.1	T_PK1
14.2.1.2	Summary of derived ASN51 plasma pharmacokinetic parameters	PK analysis	16.2.6.1.2 16.2.6.1.3	T_PK3
14.2.1.3	Summary of log-transformed derived ASN51 plasma pharmacokinetic parameters	PK analysis	16.2.6.1.2 16.2.6.1.3	T_PK4
14.2.2.1	Summary of plasma PBMC data (% above baseline)	PD analysis	16.2.6.2	T_VS1
14.2.2.2	Summary of analysis of time-matched change from baseline plasma PBMC data using analysis of variance (Day 1 vs Day 14 and Day 11 vs Day 14)	PD analysis	16.2.6.2	T_ANOVA1
14.2.2.3	Summary of ANCOVA analysis of PBMC and PK concentration to compare intercepts and slopes between Day 1 and Day 14	PD analysis	16.2.6.2	T_REGR
14.3	SAFETY DATA			
14.3.1.1	Overall summary of treatment-emergent adverse events	Safety	16.2.7.1	T_AE2
14.3.1.2	Summary of treatment-emergent adverse events	Safety	16.2.7.1	T_AE1
14.3.1.3	Summary of drug-related treatment-emergent adverse events	Safety	16.2.7.1	T_AE1
14.3.2.1	Listing of fatal adverse events	Safety	16.2.7.1	L_AE1_PG
14.3.2.2	Listing of non-fatal serious adverse events	Safety	16.2.7.1	L_AE1_PG
14.3.2.3	Listing of other significant adverse events	Safety	16.2.7.1	L_AE1_PG
14.3.3	Narratives of deaths, other serious and significant adverse events	Safety	-	-
14.3.4.1	Summary of laboratory values outside the reference range by treatment and planned relative time	Safety	16.2.8.1 16.2.8.2 16.2.8.3	T_LB1

Table	Description	Population	Source Listing	Template (Shells below)

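### Protocol 14.2 gives AE causality conflicting objects (IMP, drug/procedure, study treatment), so procedural events after dosing can be tabulated as drug-related

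*Protocol*

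**What the plan says.** Protocol section 14.2 introduces the causality item with "The assessment of relationship of AEs to the administration of IMP is a clinical decision based on all available information". The categories that follow have a wider object. Possibly related is defined as "The AE may be related to the study drug/procedure" and definitely related as "The AE is clearly related to the study drug/procedure"; the other three categories also name drug and procedure together. For regulatory reporting, possibly, probably and definitely related events "will be considered related to study treatment". The next paragraph describes related events in terms of the study drug or intervention.

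SAP section 14.2 classes a TEAE as drug-related when the investigator recorded possibly, probably or definitely. This feeds Table 14.3.1.3, "Summary of drug-related treatment-emergent adverse events".

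One arm of the trial stopping rule in protocol section 8.4.1 is "2 or more severe or clinically significant AEs considered to be at least possibly related to study treatment at any dose level"; the other is one or more SAEs at least possibly related to study treatment.

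Protocol section 6.7 anticipates discomfort, minor bleeding and bruising from arterial cannulation and, rarely, complications: for example, "a blood clot could form around the cannula".

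**The concern.** Two investigators following the same section can grade the same event in opposite ways. One who works from the lead-in asks whether ASN51 caused a cannula-site haematoma and records unrelated. One who works from the category text sees an event clearly related to a procedure and records definitely related. The SAP has no step that tells these apart, so the second grading goes into the drug-related table.

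Safety and tolerability is a secondary objective, and the groups are small enough for one event to be visible in the table. The effect would fall mainly on PET subjects, who alone have arterial lines and tracer injections. The same wording leaves open whether a procedural event can count towards section 8.4.1.

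**Working it through.** The plan states no figure on this point, so there is none to reproduce. The check is a trace of the wording and a count of exposure.

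**Object of the causality assessment, place by place**

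| Place | Object |
|---|---|
| Protocol 14.2, lead-in | administration of IMP |
| Protocol 14.2, five categories | study drug/procedure |
| Protocol 14.2, mapping for regulators | study treatment |
| Protocol 14.2, next paragraph | study drug/intervention |
| Protocol 8.4.1 | study treatment |
| Protocol 16.2.6.1, SAP 14.2, Table 14.3.1.3 | drug |

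The AE record list in protocol 14.2 has one relationship item. The AE listing shell in SAP 19.2.3 (L_AE1_PG) has one relationship column and none for procedures. Protocol 9.4.3 refers to section 14.2 when it speaks of AEs possibly related to study treatment, so the two are linked at least there. Protocol 10.1, on treatments administered, describes the tracer doses beside ASN51 while labelling the tracer a non-IMP. No passage says that study treatment excludes the tracer or procedures.

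**Exposure to arterial cannulation** (protocol 8.1.3 and 12.1)

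- PET subjects: 4 per group × 2 groups = 8.
- Sessions after the first dose: 2 each (Day 1, then session 3), so 8 × 2 = 16 cannulations at most.
- The 8 baseline cannulations precede dosing. Events from them are not TEAEs unless they worsen, so they do not belong in this count.
- Session 3 falls 3–9 days after the last dose, and the TEAE definition gives no post-dose window. If events there were not counted as treatment-emergent, 8 cannulations would remain. The range is 8 to 16.
- Arterial sampling may be reduced or removed during the study, so both are upper bounds.
- All 12 subjects also have venous cannulation on Days 1 and 14, with repeated blood sampling.

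**Effect on the drug-related table**

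Subjects are counted once. One procedural event in a subject with no other drug-related TEAE adds 1/6 = 16.7 points in a group of six, or 1/12 = 8.3 points overall. If the subject already has a drug-related TEAE, the subject-level rate does not move.

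**Stopping rule**

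The documents give no rate for qualifying procedural events. An assumed rate p per cannulation, with independence and both groups pooled, shows why no single probability can be quoted:

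P(at least 2 in 16) = 1 − (1 − p)^16 − 16p(1 − p)^15

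| Assumed p | P(at least 2 in 16) |
|---|---|
| 1% | 1.1% |
| 2% | 4.0% |
| 5% | 18.9% |
| 10% | 48.5% |

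Here p is the chance of an event that is severe or clinically significant and also graded at least possibly related. Ordinary bruising is not included. The result depends almost wholly on the assumption.

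**The case against.** The strongest reply is that the lead-in governs. Causality is to the IMP, adverse reactions in section 14.1 are defined by the IMP, and the listing column refers to drug or treatment. On that reading a cannula haematoma is unrelated and nothing goes wrong. This stands to the extent that misclassification is permitted, not required. A reader might infer that procedural events must count as drug-related; the documents do not support that. They do support two valid and opposite gradings. The eCRF is not among the documents, so it may separate the two, but the plan does not ask it to.

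A reader might also infer that routine arterial-line events would stop the trial. That does not follow. Section 8.4.1 needs an SAE, or at least two severe or clinically significant AEs, and section 6.7 describes serious complications as very rare. Section 8.4.1 does not cite section 14.2, and the mapping to study treatment is expressly for regulatory reporting. The route stays open only for rarer events, or for ones that led to an intervention, which section 14.1 would normally call significant.

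Nor is the Group 2 decision shown to be compromised. The Safety Review Group sees event descriptions and onset as well as relationship, so a cannula-site event can be recognised line by line. As scheduled, Group 1 data to Day 20 include 4 Day 1 and 3 Day 17 scans: 7 postdose arterial cannulations.

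Finally, over-attribution errs on the cautious side in an exploratory, open-label trial. That lowers the urgency but does not make the table correct.

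**Conclusion.** The concern holds as an internal contradiction that reaches a reported safety table. Applied literally, the category definitions put a procedural event after dosing into Table 14.3.1.3 as drug-related; applied from the lead-in, they do not. The exposure is at most 16 arterial cannulations in 8 PET subjects, plus venous cannulation and sampling in all 12. The effect is up to 16.7 points per event in a group of six, provided the subject has no other drug-related TEAE.

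The link to section 8.4.1 is conditional: its term study treatment is not stated to exclude procedures or tracer, and the chance of reaching the rule this way cannot be stated from the documents. The point should be corrected; it does not show that the safety review would fail.

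**What to change.** - In protocol 14.2, make the five category definitions match the lead-in (relationship to ASN51), and bring the mapping and the paragraph after it into the same terms.
- Record relationship to study procedures and to the tracer in one or two separate eCRF fields, and show them in the AE listing.
- In SAP 14.2 and Table 14.3.1.3, derive drug-related from the ASN51 field only.
- State which field the term study treatment in section 8.4.1 refers to. The passages must be reconciled; no change to the stopping threshold is proposed.

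The cost is one or two extra eCRF fields and minor wording changes in both documents. No extra procedure or sample is needed. If the eCRF already separates these items, only the wording needs to change.

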14.3 Procedures for dealing with serious adverse events

In the event of any SAE which, in the investigator’s opinion, justifies termination or modification of the trial (see section 8.4), dosing will be stopped and the sponsor’s medical monitor will be informed immediately (within 24 h of the investigator becoming aware of the event) by telephone or email, as follows.

Medical monitor: [REDACTED] MD

Tel: [REDACTED]

Mobile: [REDACTED]

Email: [REDACTED]

All SAEs occurring after the signing of the ICF until the follow up visit, regardless of study drug relationship, must be reported to the sponsor’s pharmacovigilance

department, with as much information as possible, within 24 h of the investigator becoming aware of the event. The investigator will complete an SAE form and provide it to the sponsor's pharmacovigilance department, via the following contact details.

Monitor: [REDACTED] MD

Tel: [REDACTED]

Mobile: [REDACTED]

Email: [REDACTED]

The sponsor will also be notified by email [REDACTED]
[REDACTED]

The investigator will notify the REC of SAEs that occur during this trial, if applicable, in accordance with the SOPs issued by the Research Ethics Service (RES)²³.

The sponsor is responsible for determining the expectedness of the event, using the reference safety information in the IB¹. The sponsor will notify the MHRA of all suspected unexpected serious adverse reactions (SUSARs), and will be responsible for ensuring that the REC is notified of SUSARs, if applicable. SUSARs that are fatal or life-threatening must be notified to the MHRA and REC within 7 days after the sponsor has learned of them. Other SUSARs must be reported to the REC and MHRA within 15 days after the sponsor has learned of them.

If a subject has an SAE during the study, they will have an additional telephone follow-up as described in section 12.3.

